## **Summary of Changes from Previous Version:**

Version Information	Summary of Revisions Made	Rationale
V2 10/13/2025	
 
Section D, Inclusion Criteria:** Added PHQ-9 to inclusion criterion #8.
 
Section D, Exclusion Criteria (#4):** Revised to read: "Drug or alcohol intoxication (based on a positive UTOX or breathalyzer test at screening or study session), or reported alcohol/drug withdrawal. Last cannabis use must be >48 hours prior to the study session."
 
	
 
To accommodate the practical screening procedures and maintain consistency with a previous project. PHQ-9 is included in the NeuroMAP Core data collection, which all participants will be recruited through (Section E). A PHQ-9 score ≥10 is considered equivalent to a MADRS score ≥15 in depressive severity.
 
To make the exclusion condition more practical and operationally.
 

- 3. Section D, Exclusion Criteria (#9):\*\*
  Removed the criterion: "Prescription of a medication outside of the accepted range, as determined by the best clinical practices and current research."
- 4. Section F, Table 1:\*\* Moved the clinicianadministered depression and mania assessments (MADRS and YMRS) to the day of scanning.
- 5. Section F, Figure 1:\*\* Removed the second resting-state scan from the MRI session.
- 6. Section F, Think and Regulate Affective States Task (TReAT):\*\* Increased the number of attention trials from four 3-second trials to six 2-second trials.
- 7. Section J, Psychiatric or Behavioral Risk:\*\*
  Added "Current DSM-5 diagnosis of" before
  "moderate-to-severe substance use disorder."

- 3. This exclusion is beyond the scope of the study's monitoring and cannot be reliably assessed within the study's procedures.
- 4. To ensure that symptom ratings reflect participants' clinical status at the time of imaging, as symptoms may change between the preparation visit and the scan day.
- 5. To ensure the total MRI session is completed in under two hours and to prioritize scans most relevant to the study aims. The second resting-state scan was deemed least essential.
- 6. To increase task demand and more effectively clear participants' thought states between affective task periods.
- 7. To clarify and specify the diagnostic basis for determining exclusion due to substance use disorder.

## A. Purpose of the Study

The purpose of this study is to investigate the neural mechanisms underlying mood instability in individuals with bipolar disorder (BD) by decoding moment-to-moment emotional states using functional magnetic resonance imaging (fMRI) and advanced computational methods. Mood instability is a defining and impairing feature of BD, yet its dynamic neurobiological underpinnings remain poorly understood.

This research seeks to understand how emotional states fluctuate over time, how these fluctuations differ between individuals with BD and healthy controls (HC), and how the brain supports or disrupts emotional self-regulation. Findings from this study are expected to inform the development of personalized, neurobiologically informed treatments that adapt to an individual's emotional state.

## **B. Specific Aims**

- (1) Decode momentary emotional states from whole-brain fMRI data using machine learning.
- (2) Quantify dynamic fluctuations in brain state using complexity science (e.g., metastability, fractal scaling) and network control theory.
- (3) Evaluate the impact of positive emotion amplification strategies on emotional state stability and associated brain dynamics in BD.

**Hypothesis 1**: A machine learning classifier can decode different thinking states with statistically significant accuracy from fMRI brain activation signals. The decoded state trajectory in BD will be more unstable and fluctuating (i.e., exhibit greater temporal irregularity) compared to healthy controls (HC).

**Hypothesis 2**: Individuals with BD will exhibit more unstable emotional state trajectories (lower metastability and fractal scaling) compared to HC.

**Hypothesis 3**: Positive affect amplification will stabilize emotional dynamics and engage cognitive control regions in BD participants.

The outcome of these aims will help the investigators develop a personalized intervention approach to stabilize mood fluctuations.

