# C. Background and Significance

Bipolar disorder (BD) is a serious mental health condition marked by significant mood instability, which impairs emotion regulation and leads to functional difficulties [1]. Unlike unipolar depression, BD involves rapid and intense mood fluctuations, including difficulty sustaining negative emotions [2]. These patterns suggest that BD is defined more by dynamic instability than by persistent mood states.

Neuroimaging studies have revealed abnormalities in emotion-related brain circuits, including decreased activity in regulatory regions like the anterior cingulate cortex (ACC) and prefrontal cortex (PFC), and increased activity in emotion response regions (e.g., amygdala) [3, 4]. BD is also associated with altered connectivity in the default mode and frontoparietal networks [5]. Dynamic functional connectivity studies show increased variability in brain states, but these methods are limited by low temporal resolution and interpretability [6, 7].

To address these gaps, this study will decode emotional states from whole-brain fMRI patterns using machine learning [8, 9] and quantify emotional dynamics using complexity science and network control theory [10, 11]. We will also evaluate how positive emotion amplification strategies influence emotional stability, informed by evidence from Amplification of Positivity (AMP) psychotherapy and neurofeedback [12, 13]. This approach offers a novel framework for understanding mood instability in BD and identifying targets for personalized, adaptive interventions.

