## **HC Group:**

9. No current or past psychiatric disorder (verified by MINI)

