#### **Exclusion Criteria**

- 1. No telephone or easy access to telephone
- 2. Significant medical problems as identified by the medical screening questionnaire: e.g. a history of unstable liver or renal insufficiency; glaucoma; significant and unstable cardiac, vascular, pulmonary, gastrointestinal, endocrine, neurologic, hematologic, rheumatologic, or metabolic disturbance; or any other condition that, in the opinion of the investigator, would make participation not be in the best interest (e.g., compromise the well-being) of the participant or that could prevent, limit, or confound the protocol-specified assessments
- 3. A positive test for drugs of abuse, including alcohol (breath test), cocaine, opiates, amphetamines, methamphetamines, phencyclidine, benzodiazepines, barbiturates, methadone, and oxycodone
- 4. Drug or alcohol intoxication (based on positive UTOX or breathalyzer test at screening or study session) or reported alcohol/drug withdrawal, last cannabis use must be >48 hours prior to study session.
- 5. Current DSM-5 diagnosis of a psychosis spectrum disorder or moderate to severe substance use disorder
- 6. Moderate to severe traumatic brain injury or other neurocognitive disorder with evidence of neurological deficits, neurological disorders, or severe or unstable medical conditions that might be compromised by participation in the study (to be determined by primary care provider)
- 7. Current significant suicidal ideation or suicide attempt within the past 3 months.

- 8. Change in the dose or prescription of a medication within the 6 weeks before enrolling in the study that could affect brain functioning, e.g., anxiolytics, antipsychotics, antidepressants, or mood stabilizers
- 9. Taking drugs that affect the fMRI hemodynamic response (e.g., methylphenidate, acetazolamide, excessive caffeine intake > 1000 mg/day)
- 10. MRI contraindications as documented on the MR Environment Screening
- 11. Unwillingness or inability to complete any of the major aspects of the study protocol, including magnetic resonance imaging (i.e., due to claustrophobia), or behavioral assessment. However, failing to complete some individual aspects of these assessment sessions will be acceptable (i.e., being unwilling to answer individual items on some questionnaires or being unwilling to complete a behavioral task)
- 12. Non-correctable vision or hearing problems

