## Think and Regulate Affective states Task (TReAT)

Figure 1 (lower panel) illustrates the sequence of the Think and Regulate Affective states Task (TReAT). TReAT consists of seven types of blocks. In the **Think** block, a short description (keywords) of an autobiographical event is presented, and participants engage in self-relevant emotional thoughts for 20 seconds. These keywords are provided by the participants using a thought collection worksheet (study-specific) during Visit 1. The Think block is followed by a **Rating** block, during which participants use the Affective Slider [18] to rate valence and arousal based on the preceding Think block while viewing the same keywords. Eight seconds (four per measure) are provided for responses. In the **Regulation** block, participants are instructed to amplify positive mood for 20 seconds while continuing to view the same keywords. At the end of this block, another **Rating** block is presented for eight seconds to assess the affective state during the Regulation block. In the **Attention** block, an array of five arrows is presented, and participants must respond to the direction of the center arrow within two seconds per trial; each block contains six trials. In the Rest block (**Rest**), a fixation cross is displayed for 16 seconds, during which participants are instructed to clear their minds and avoid directed thoughts. A **Rating** block follows the Rest block to assess the affective state during resting. These blocks will be repeated eight times in one fMRI scan run, and four runs will be performed.

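### Does Hypothesis 1 mistake decoder error for emotional instability if decoding accuracy differs between the bipolar and control groups?

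*Protocol*

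**What the plan says.** Hypothesis 1 in Section B makes two predictions. The first is that a machine learning classifier "can decode different thinking states with statistically significant accuracy". The second is the group contrast: "The decoded state trajectory in BD will be more unstable and fluctuating (i.e., exhibit greater temporal irregularity) compared to healthy controls (HC".

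Hypothesis 2 is separate. It concerns emotional state trajectories and names its own measures, metastability and fractal scaling. Section A describes the study as a whole: it investigates what underlies "mood instability in individuals with bipolar disorder (BD) by decoding moment-to-moment emotional states".

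Three other places bear on the point:

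- Section D, exclusion criterion 8, removes people with a "Change in the dose or prescription of a medication within the 6 weeks before enrolling in the study that could affect brain functioning". Stable medication is therefore allowed. Controls must have no psychiatric history.
- Section C reports "decreased activity in regulatory regions like the anterior cingulate cortex (ACC) and prefrontal cortex (PFC") in BD. The same sentence goes on to report increased activity in emotion-response regions such as the amygdala.
- Section F (TReAT) has participants use a slider "to rate valence and arousal based on the preceding Think block".

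The protocol has no statistical analysis section. It names no classifier, irregularity index, accuracy level or accuracy by group.

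**The concern.** Decoder mistakes look like state changes. If the classifier is less accurate in one group, that group's decoded trajectory flickers more, even when the underlying emotions are equally steady.

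The protocol gives reasons why the signal might differ between the groups: stable psychotropic medication in BD and altered regional activity. The only property of the decoder that Hypothesis 1 mentions is accuracy better than chance, which says nothing about equal accuracy in the two groups. Motion monitoring, physiological correction and drug screening reduce noise but do not equalise accuracy.

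If Hypothesis 1 does treat decoded irregularity as mood instability, its main group comparison could be positive, null or reversed for reasons unrelated to emotion.

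**Working it through.** **1. The plan's own figure.** The protocol gives no accuracy figure to reproduce. Its one design figure is in Rationale for Sampling Plan: 80% power with 32 per group at d = 0.71. Assuming a two-sided 5% level, power = Φ(0.71 × √(32/2) − 1.96) = Φ(0.88) = 81.1%; the t-test gives 79.8%. The figure reproduces, but it is tied to measures like fractal scaling and does not bear on decoder accuracy.

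**2. The mechanism.** Assume two states, accuracy p, independent errors and true switch rate s. Then

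decoded switch rate = 2p(1−p) + s(2p−1)².

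- p = 0.80, s = 0: 2 × 0.80 × 0.20 = 0.320
- p = 0.75, s = 0: 2 × 0.75 × 0.25 = 0.375
- Share of a true difference passed on, (2p−1)²: 0.36 at p = 0.80 and 0.25 at p = 0.75

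Decoded irregularity does depend on accuracy.

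**3. The size.** From the protocol: 32 per group, and 8 × 4 = 32 Think blocks of 20 seconds. Assumed: 2-second sampling (10 volumes per block), no true switching, all accuracies, and a between-person accuracy SD of 5 to 10 points. The table gives the share of simulated trials with a significant result.

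| Setting (HC vs BD accuracy) | Result | Share |
|---|---|---|
| 80% vs 75%, hard labels, independent errors | BD more irregular | 44–93% |
| Same, error correlation 0.5 | BD more irregular | 43–84% |
| Same, error correlation 0.95 | BD more irregular | 22–25% |
| 80% vs 78%, hard labels, correlation 0 or 0.5 | BD more irregular | 10–29% |
| 75% vs 80%, hard labels, correlation 0 or 0.5 | BD less irregular | 43–92% |
| 80% vs 75%, calibrated probabilities, correlation 0 or 0.5 | BD *less* irregular | 12–77% |
| Equal accuracy | either direction | about 3% each |

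A repeat of the hard-label runs agreed closely. It also gave about 7% for 65% vs 60% at error correlation 0.95. The last two 80% vs 75% entries matter most: for one and the same accuracy gap, the direction of the artefact depends on whether the index uses hard labels or probabilities. The protocol does not fix that choice.

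**4. The text.** The grammatical subject of the second prediction is the decoded state trajectory. The parenthesis defines unstable and fluctuating, for that trajectory, as temporal irregularity. The sentence does not say that decoded irregularity is emotional instability; emotional state trajectories is the wording of Hypothesis 2. Rewording Hypothesis 1 so that its outcome is irregularity of the decoded trajectory would leave it as it stands. Better-than-chance accuracy is the first of two predictions, and nothing makes it sufficient for interpreting the second.

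**5. Would a safeguard in the hypothesis be harmless?** One candidate rule calls a positive result unresolved when the accuracy gap is large enough to explain it. Accuracy can only be scored against the instructed state, so real drift of thought also lowers it. Let a be decoder fidelity and q the share of time truly off the instructed state. Scored accuracy is A = (1−q)a + q(1−a), and the irregularity that A alone would imply is

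2A(1−A) = 2a(1−a) + 2q(1−q)(2a−1)².

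The observed value is 2a(1−a) + s(2a−1)². When drift is positively autocorrelated, s does not exceed 2q(1−q), so the implied value is at least the observed one.

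Take a = 0.80 with q = 0.10 and s = 0.10 in BD (assumed), and no drift in HC. Then A = 0.9 × 0.8 + 0.1 × 0.2 = 0.74 in BD against 0.80 in HC. Implied irregularity in BD is 2 × 0.74 × 0.26 = 0.385; observed is 0.320 + 0.10 × 0.36 = 0.356. A genuine effect would be called unresolved.

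In simulation (fidelity 0.80 in both groups, more real drift in BD, 32 per group) the rule did this to 93–100% of correct significant results with independent errors. With an error correlation of 0.5 known to the analyst it was 0–8%. The rule depends on an error structure that is not known in advance.

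**The case for a change.** The strongest reply is that Section A makes decoded states the route to mood instability, so a reader will take a positive Hypothesis 1 as evidence of instability whatever its grammar. Under a second set of assumptions (true switching 0.10 in both groups, accuracy 70% in BD and 75% in HC) the artefact reached d of about 0.84, above the 0.71 used for sizing. The accuracy condition is also weak. With 64 participants, two classes and an SD of 5 to 10 points, mean accuracy is significant from 0.5 + t(63) × SD/8, about 51.2% to 52.5%. Tabulating accuracy by group would cost little.

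Much of this stands as advice on interpretation. Anyone reporting Hypothesis 1 should show decoding accuracy by group beside the irregularity result and look at head motion. It does not stand as a fault in the protocol. Section A states a general purpose and sets no inferential rule. The 51.2–52.5% bar comes from assumed inputs. Allowing stable medication makes an accuracy gap possible but does not show one, and activity changes that go down in some regions and up in others do not establish lower decodability. Accuracy by group, a motion sensitivity analysis and a reporting rule are details commonly left to an analysis plan.

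**Conclusion.** The concern does not hold. Unequal accuracy can distort a comparison of decoded trajectories (0.320 against 0.375 in the simplest case), but Hypothesis 1 claims only that the decoded trajectory is more irregular in BD. It does not make above-chance accuracy the warrant for reading that as mood instability.

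The harm needs an accuracy gap that nothing in the protocol documents. Its size rests on assumed accuracies, SDs, sampling interval, error correlation and index. Across those assumptions the false-positive share runs from about 7% to 93%, and the sign can flip. What remains is a caution for the analysis plan and the eventual report. This conclusion rests on the protocol alone; the analysis plan was not available.

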## D. Criteria for Participant Selection

#### Target Recruitment:

- 32 individuals with BD (BD-I or BD-II, currently in a depressive or mixed state)
- 32 healthy control participants

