#### Rationale for Sampling Plan

A final sample size of 32 per group (after accounting for  $\sim$ 10% attrition) provides sufficient power (80%) to detect a medium effect size (d = 0.71) based on pilot findings, particularly in measures like fractal scaling.

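### Does the 80% power fail to cover Hypothesis 2 because the hypothesis names two metrics, and does the protocol contradict itself on the direction of metastability?

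*Protocol*

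**What the plan says.** Section B, Aim 2, sets the task: "Quantify dynamic fluctuations in brain state using complexity science (e.g., metastability, fractal scaling) and network control theory". The two complexity metrics are given there as examples. Hypothesis 2 then makes the group prediction: "Individuals with BD will exhibit more unstable emotional state trajectories (lower metastability and fractal scaling) compared to HC". Hypothesis 1 concerns a different object, the state trajectory decoded by the classifier, which is expected to be "more unstable and fluctuating (i.e., exhibit greater temporal irregularity") in bipolar disorder (BD) than in healthy controls (HC).

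The only power statement is under Rationale for Sampling Plan in section D. The final 32 per group "provides sufficient power (80%) to detect a medium effect size (d = 0.71) based on pilot findings, particularly in measures like fractal scaling". It gives no alpha, no separate effect size for metastability, and no rule for combining metrics. Metastability is not defined anywhere in the protocol.

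**The concern.** Two things catch the eye.

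First, Hypothesis 2 joins two metrics with the word and, while the sample size rests on one standardised difference. If the hypothesis counted as confirmed only when both metrics were significantly lower, the chance of success would be below the stated 80%. If one of the two were enough, each tested at 5%, the chance of a false claim would exceed 5%. Either way the stated power would not describe the test that decides the hypothesis, and the sponsor could pick the metric that worked.

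Second, Aim 2 uses metastability to describe fluctuation, and Hypothesis 1 expects more fluctuation in BD. Hypothesis 2 nevertheless expects metastability to be lower. A reader who takes metastability to rise with fluctuation sees a reversed sign, and may fear that a difference in either direction could be presented as support.

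**Working it through.** **Inputs from the protocol (section D):** n = 32 per group, d = 0.71, power 80%, equal groups.

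**Assumptions, because the protocol is silent:** two-sided alpha of 0.05; for the two-metric scenarios, a metastability effect of 0.71, 0.50 or 0.40 and a correlation between the metrics of 0 to 0.9.

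**1. Reproduce the stated figure.**
- Normal approximation: n = 2(1.960 + 0.842)² / 0.71² = 2 × 7.85 / 0.504 = 31.1, rounded up to 32 per group.
- Power at n = 32: the standardised mean difference is 0.71 × √(32/2) = 2.84, and Φ(2.84 − 1.96) = Φ(0.88) = 81.1%.
- The exact two-sample t-test gives 79.8%.
- A one-sided 5% test would need only 25 per group, so it does not fit.

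The statement is therefore correct for one two-sided comparison on one measure, which is how it is worded.

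**2. What follows if both metrics must be significant (n = 32, each at two-sided 0.05).**
With correlation 0 and both effects at 0.71, joint power is 0.798² = 63.7%. Simulated correlated t-tests (200,000 replicates) give:

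| Metastability effect | Correlation 0 | 0.5 | 0.9 |
|---|---|---|---|
| 0.71 | 63.7% | 68.5% | 74.7% |
| 0.50 | 40.2% | 45.7% | 50.1% |
| 0.40 | 28.0% | 32.6% | 35.0% |

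**3. What follows if either metric suffices.**
- With no adjustment and independent metrics, the false-positive rate is 1 − 0.95² = 9.75%. Simulation gives 9.1% at correlation 0.5 and 7.2% at 0.9.
- With a Bonferroni split (0.025 each) the error is held at 5% or less. Power for one metric at 0.025 is 70.6%. For at least one of two independent metrics, both with effect 0.71, it is 1 − (1 − 0.706)² = 91.3%. At other values:

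| Metastability effect | Correlation 0 | 0.5 | 0.7 | 0.9 |
|---|---|---|---|---|
| 0.71 | 91.3% | 85.0% | 81.6% | 76.9% |
| 0.50 | 81.9% | 75.6% | 73.2% | 70.8% |
| 0.40 | 77.9% | 72.8% | 71.3% | 70.5% |

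The power for Hypothesis 2 can thus lie well below 80% or above it. What moves it is the decision rule, the metastability effect and the correlation, and the protocol states none of these. No stated figure is contradicted.

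**4. Direction, with the statements side by side.**
- Aim 2 says that metastability and fractal scaling are used to quantify fluctuations. Using a metric to quantify something does not say whether the metric rises or falls with it. Fractal scaling stands in the same list and is also predicted to be lower.
- Hypothesis 1 speaks of temporal irregularity in the decoded trajectory and does not mention metastability.
- Section C reports greater variability of brain states in BD from dynamic functional connectivity studies. It does not link this to metastability.
- Hypothesis 2 is the only place where metastability is given a sign, and the sign is lower.

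With one statement of direction there is nothing for it to conflict with. To call it reversed, one would have to bring in a definition of metastability from outside the protocol.

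**The case for a change.** The strongest case for the concern is that the hypothesis and the sample-size rationale are both protocol text, and that on a literal reading of and the hypothesis is not the one that was powered. No later analysis plan can restore 80% for a joint claim at 32 per group: about 42 per group would be needed at correlation 0 and about 40 at correlation 0.5, even with both effects at 0.71. The protocol also never explains why lower metastability should mean more instability.

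The arithmetic stands, and so does the observation that 80% is a single-comparison figure. The reading does not follow. The bracket in Hypothesis 2 can equally be taken as a list of two indicators of instability, and nothing there or in section D says that both must reach significance. The sampling rationale refers to effects "based on pilot findings, particularly in measures like fractal scaling", which is a claim about single measures and is not tied to one metric alone.

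A definition of metastability with a sentence on its expected sign would help a reader. Its absence leaves something unexplained but contradicts nothing. The fear that either sign could be claimed as support is answered by Hypothesis 2, which commits to one. A directional prediction can also be tested two-sided, and the sample size matches a two-sided test.

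Making fractal scaling the only confirmatory outcome would be defensible, but it is a preference. The protocol does not label Hypothesis 2 as its main hypothesis. It describes a cross-sectional imaging study (section F) that is also meant to supply preliminary data for later funding (section N).

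**Conclusion.** The concern does not hold. The stated 80% is a per-measure figure and is right to rounding: 32 per group by the normal approximation, 79.8% by the t-test, assuming a two-sided alpha of 0.05. The lower power of about 64% to 75%, and the false-positive rate of about 7% to 10%, are correct only under decision rules that the protocol does not contain; the power range also assumes a metastability effect of 0.71. An error-controlled either-metric rule keeps about 77% to 91% under that same effect, and about 71% to 82% if the metastability effect is 0.50. Metastability has one stated direction and no conflicting one.

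What remains is that the protocol does not say which metric is decisive or how two metrics are combined. That is commonly fixed in the SAP, which was not available here, so its absence from the protocol is not a defect. Whether 32 per group will in fact remain after attrition is a separate question and has no bearing on this one.
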